Since patients who discontinue the treatment with the IMP will not be withdrawn from the study but will be asked to complete safety and efficacy assessments as per the protocol, missing data under treatment policy strategy will be addressed by modeling patients with missing data after retrieved drop-outs (based on assumption of missing data would have been like retrieved drop-outs if they were assessed). Retrieved drop-out patients are defined as patients who discontinue study treatment and decide to remain in the study by following the schedule of assessments and continuing to adhere to protocol requirements.

If enough retrieved drop-out data are available to allow convergence of a regression model, a Multiple Imputation model based on retrieved drop-outs (MI-RD) will be used for analysis. Specifically, MI will be performed based on the subjects' allocated treatment arm and observed values (baseline and intermediate) as covariates in a regression model using data from subjects that discontinued the treatment but have the primary endpoint measurement with gender, and age class as covariates. For each co-primary endpoint, MI-RD will be implemented into different steps:

- Intermittent missing data up to primary time point (Week 4 for Schirmer I test, and Week 12 for SANDE) will be imputed using MCMC methods assuming missing at random (MAR) data;
- The remaining missing values with a monotone missing data pattern will be imputed based on observed data of retrieve dropouts;

- the fully imputed datasets will be analyzed and results will be combined using Rubin's to draw inference.

If not enough data was retrieved after study treatment discontinuation for assure the convergence of the MI-RD regression model (the final decision will be done at the time of the analysis and reported in the CSR; different approaches might be used for the two coprimary endpoint), the same model will be fit using data from subjects of control group, washing-out the effect of treatment; this approach does not assume benefits for cenegermin in case of discontinuation and limits a post-discontinuation clinical effect to that of vehicle. Specifically, wash-out approach will be implemented in this way:

- Intermittent missing data up to primary time point (Week 4 for Schirmer I test, and Week 12 for SANDE) will be imputed using MCMC methods assuming MAR;

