4.7 Eligible eye

Assuming that all the inclusion/exclusion criteria are met in both eyes, the worse eye (eligible eye) will be determined at the baseline visit using a stepladder approach, as follows:

1. Schirmer’s Test: worse eye determined as eye with lower Schirmer I score.
2. NEI score: if Schirmer I score is the same in both eyes, worse eye will be determined by NEI score (cornea + conjunctival staining).

If all the above are identical, determination of the worse eye will be based on the investigator’s judgement, otherwise the right eye will be used as the eligible eye.

5. Sample size justification

The sample size of the study is calculated based on results from previous studies.

Sample size was calculated according to the following assumptions:

- randomization ratio 1:1.
- a difference of 30% in Schirmer I rate of responders (value >10mm/5min at week 4.) in favor of rhNGF treatment at Week 4, with a responder rate of 5% for vehicle.
- 15 points in Global SANDE score improvement at Week 12, with a standard deviation of 20 points.

Based on these assumptions, a total sample size of 90 evaluable patients (100 pts considering 10% of patients not evaluable after enrollment) allows to achieve an overall power of 90% to show superiority of rhNGF eye drops solution vs vehicle in terms of both co-primary endpoints, considering a one-sided alpha of 0.025. Specifically:

- A power of 95.8% is achieved for Schirmer I primary endpoint.
- A power of 94.0% is achieved for SANDE primary endpoint.

6. Randomization and blinding

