If there are not enough retrieved dropouts for convergence of MI-RD regression model, a reference-based Multiple Imputation (MI) approach will be adopted to consider a missing not at random (MNAR) mechanism for missing data: imputation of values in the rhNGF arm (above step #2) will be done using the non-missing values from the control group (this approach will be referred as "Copy Reference"). This approach does not assume benefits for rhNGF in case of discontinuation and limits a post-discontinuation clinical effect to that of vehicle. The final decision on the use of the MI-RD vs Copy-Reference for this endpoint will be done at the time of the analysis and reported in the CSR.

Whether for MI-RD or Copy-Reference approach, the adjusted estimated treatment differences in proportions between cenegegermin and vehicle at week 4 will be displayed together with the corresponding two-side 95% confidence intervals and p-value.

10.1.2.2 Change from baseline in the global SANDE score at week 12

This co-primary endpoint will be analyzed by means of an Analysis of Covariance (ANCOVA) adjusting by pre-defined baseline factors (gender, age class, baseline global SANDE score as fixed effects and site as random effect) and a one-sided test will be used to test for differences between treatment groups. Rules for derivation of SANDE scores are reported in section 12.2.

For the imputation of missing data, a regression model will be created by including the baseline global SANDE score, gender, age class, and intermediate global SANDE scores up to week 12. Two hundred data sets will be generated, and the random seed number will be 37103939. MI will be implemented in the following steps:

1. Partial imputation assuming MAR will be carried out to impute intermittent (non-monotone) missing data of global SANDE score based on a multivariate joint Gaussian imputation model using the MCMC method. A separate imputation model will be used for each treatment arm. In case of non-convergence or non-estimability issues, a single imputation model will be considered (with treatment arm added as explanatory variable to the model). A total of 200 datasets will be created. These datasets will be utilized in Step #2.
2. The remaining monotone missing data will be imputed using a MI regression including the same explanatory variables of the previous step. According to MI-RD approach, only non-missing values from retrieve dropouts will be used to inform the regression model.

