15.5 SAS Code for the primary analysis

15.5.1 Schirmer I test >10mm/5min at week 4

Standard	Alternative code in case of no convergence
<pre> PROC MI DATA= EFFICACY01 NIMPUTE=200 SEED=820520 OUT=EFFICACY_MONO1; VAR BASVAL SCHIRMER_W2 AVAL; MCMC CHAIN=SINGLE NBITER=200 NITER=100 IMPUTE=MONOTONE; WHERE TRT=1; RUN; PROC MI DATA=EFFICACY01 NIMPUTE=200 SEED=820520 OUT=EFFICACY_MONO2; VAR BASVAL SCHIRMER_W2 AVAL; MCMC CHAIN=SINGLE NBITER=200 NITER=100 IMPUTE=MONOTONE; WHERE TRT=2; RUN; DATA EFFICACY_MONO; SET EFFICACY_MONO1 EFFICACY_MONO2; RUN; </pre>	<pre> PROC MI DATA= EFFICACY01 NIMPUTE=200 SEED=820520 OUT=EFFICACY_MONO; VAR BASVAL TRT SCHIRMER_W2 AVAL; MCMC CHAIN=SINGLE NBITER=200 NITER=100 IMPUTE=MONOTONE; RUN; </pre>
<pre> PROC SORT; BY _IMPUTATION_ SUBJID; RUN; </pre>	
<pre> PROC MI DATA=EFFICACY_MONO SEED=200582 NIMPUTE=1 OUT=EFFICACY_IMP; BY _IMPUTATION_; CLASS TRT AGE SEX EOTSTT; MONOTONE REG(AVAL = TRT AGE SEX BASVAL / DETAILS); MNAR MODEL(AVAL / MODELOBS= (EOTSTT='NOT COMPLETED')); VAR TRT AGE SEX BASVAL SCHIRMER_W2 AVAL; RUN; </pre>	<pre> PROC MI DATA=EFFICACY_MONO SEED=200582 NIMPUTE=1 OUT=EFFICACY_IMP; BY _IMPUTATION_; CLASS TRT AGE SEX EOTSTT; MONOTONE REG(AVAL = TRT AGE SEX BASVAL / DETAILS); MNAR MODEL(AVAL / MODELOBS= (TRT=2 /*Vehicle*/)); VAR TRT AGE SEX BASVAL SCHIRMER_W2 AVAL; RUN; </pre>

Standard	Alternative code in case of no convergence
<pre> DATA EFFICACY_IMP; SET EFFICACY_IMP; IF AVAL>10 THEN AVALC='Y'; ELSE AVALC='N'; RUN; ODS OUTPUT DIFFS=GLIMMIX_DIFFS; ODS OUTPUT PARAMETERESTIMATES=ESTIMATES; PROC GLIMMIX DATA=EFFICACY_IMP METHOD = QUAD; BY _IMPUTATION_; CLASS TRT(REF="1") AGE(REF="<=XX") SEX(REF="F") SITEID; MODEL AVALC(EVENT='Y')=TRT AGE SEX BASVAL /S DIST=BINARY LINK=LOGIT OR; RANDOM INTERCEPT / SUBJECT=SITEID; LSMEANS TRT / ILINK ODDSRATIO CL DIFF; RUN; ODS OUTPUT PARAMETERESTIMATES=POOLED_ESTIMATES; PROC MIANALYZE PARMS = ESTIMATES ; CLASS TRT AGE SEX; MODELEFFECTS INTERCEPT TRT AGE SEX BASVAL ; RUN; ODS OUTPUT PARAMETERESTIMATES=POOLED_DIFFS; PROC MIANALYZE DATA = GLIMMIX_DIFFS ; MODELEFFECTS ESTIMATE; STDERR STDERR; RUN; DATA POOLED_ODDS_RATIO; SET POOLED_DIFFS; ODDSRATIO=EXP(ESTIMATE); ODDS_95LL=EXP(LCLMEAN); ODDS_95UL=EXP(UCLMEAN); RUN; </pre>	

15.5.2 Change from baseline in the global SANDE score at week 12

Standard	Alternative code in case of no convergence

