<pre> PROC MI DATA= EFFICACY01 NIMPUTE=200 SEED=37103939 OUT=EFFICACY_MONO1; VAR BASVAL SANDE_W2 SANDE_W4 SANDE_W8 AVAL; MCMC CHAIN=SINGLE NBITER=200 NITER=100 IMPUTE=MONOTONE; WHERE TRT=1; RUN; PROC MI DATA=EFFICACY01 NIMPUTE=200 SEED=37103939 OUT=EFFICACY_MONO2; VAR BASVAL SANDE_W2 SANDE_W4 SANDE_W8 AVAL; MCMC CHAIN=SINGLE NBITER=200 NITER=100 IMPUTE=MONOTONE; WHERE TRT=2; RUN; DATA EFFICACY_MONO; SET EFFICACY_MONO1 EFFICACY_MONO2; RUN; </pre>	<pre> PROC MI DATA= EFFICACY01 NIMPUTE=200 SEED=37103939 OUT=EFFICACY_MONO; VAR BASVAL TRT SANDE_W2 SANDE_W4 SANDE_W8 AVAL; MCMC CHAIN=SINGLE NBITER=200 NITER=100 IMPUTE=MONOTONE; RUN; </pre>
<pre> PROC SORT; BY _IMPUTATION_ SUBJID; RUN; </pre>	
<pre> PROC MI DATA=EFFICACY_MONO SEED=200582 NIMPUTE=1 OUT=EFFICACY_IMP; BY _IMPUTATION_; CLASS TRT AGE SEX EOTSTT; MONOTONE REG(AVAL = TRT AGE SEX / DETAILS); MNAR MODEL(AVAL / MODELOBS= (EOTSTT='NOT COMPLETED')); VAR TRT AGE SEX BASVAL SANDE_W2 SANDE_W4 SANDE_W8 AVAL; RUN; </pre>	<pre> PROC MI DATA=EFFICACY_MONO SEED=200582 NIMPUTE=1 OUT=EFFICACY_IMP; BY _IMPUTATION_; CLASS TRT AGE SEX EOTSTT; MONOTONE REG(AVAL = TRT AGE SEX / DETAILS); MNAR MODEL(AVAL / MODELOBS= (TRT=2 /*Vehicle*/)); VAR TRT AGE SEX BASVAL SANDE_W2 SANDE_W4 SANDE_W8 AVAL; RUN; </pre>

Standard	Alternative code in case of no convergence
<pre>ODS OUTPUT DIFFS=DIFFS; ODS OUTPUT PARAMETERESTIMATES=ESTIMATES; PROC MIXED DATA=EFFICACY_IMP; BY _IMPUTATION_; CLASS TRT(REF="1") SEXC(REF="F") SITEID; MODEL AVAL=TRT AGE SEXC BASVAL /S; RANDOM INTERCEPT / SUBJECT=SITEID; LSMEANS TRT / CL DIFF; RUN; ODS OUTPUT PARAMETERESTIMATES=POOLED_ESTIMATES; PROC MIANALYZE PARMS = ESTIMATES ; CLASS TRT SEXC; MODELEFFECTS INTERCEPT TRT AGE SEXC BASVAL ; RUN; ODS OUTPUT PARAMETERESTIMATES=POOLED_DIFFS; PROC MIANALYZE DATA = DIFFS ; MODELEFFECTS ESTIMATE; STDERR STDERR; RUN;</pre>

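### The Copy Reference code for both co-primaries keeps a treatment term that vehicle-only donors cannot estimate, so it delivers the promised vehicle-based imputation only if the software zeroes that term

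*SAP*

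**What the plan says.** The primary method for missing co-primary data is multiple imputation informed by retrieved dropouts (MI-RD). If there are too few of them for the model to converge, SAP 10.1.2.1 and 10.1.2.2 switch to Copy Reference, in which missing cenegermin values are imputed from vehicle data. SAP 10.1.2.1 states the purpose: the approach "limits a post-discontinuation clinical effect to that of vehicle". Protocol 9.4.3.1 describes the same fallback: "the same model will be fit using data from subjects of control group, washing-out the effect of treatment".

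The code is in the right-hand (alternative) column of SAP 15.5. TRT, age class and sex are class variables in both blocks.

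- SANDE (15.5.2): "MONOTONE REG(AVAL = TRT AGE SEX / DETAILS); MNAR MODEL(AVAL / MODELOBS= (TRT=2 /*Vehicle"
- Schirmer (15.5.1): "MONOTONE REG(AVAL = TRT AGE SEX BASVAL / DETAILS); MNAR MODEL(AVAL / MODELOBS= (TRT=2 /*Vehicle"

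In both blocks TRT also stands in the VAR list.

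On covariates, the prose has step 2 reuse the explanatory variables of step 1. For Schirmer it names sex, age class, and the baseline and week 2 values. For SANDE it names sex, age class, baseline and the intermediate scores up to week 12. The opening of 10.1.2 also makes the allocated arm an imputation covariate, and no sentence removes it for Copy Reference.

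**The concern.** MODELOBS restricts the fit to vehicle patients, while the model being fitted contains treatment. Donors who all share one treatment carry no information on a treatment coefficient. Predicting for a cenegermin patient, which is what the fallback is for, nevertheless calls on that coefficient.

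The result then rests on how the program resolves a redundant column. It may give the intended vehicle prediction, a failed step, or a value set by the coding of TRT and not by data. Neither document says how the redundancy is to be handled.

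This is the pre-specified fallback for both co-primaries, and both must succeed. The week 8 Schirmer and the SANDE severity and frequency key secondaries refer back to the same method (SAP 10.2.2.1 to 10.2.2.3). The choice between MI-RD and Copy Reference is made at the time of analysis, which under SAP 6.2 follows lock and unblinding. A repair to failing code would then be made with treatment codes available.

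**Working it through.** **Planned figures (SAP section 5).** The documents give no figure for the imputation code itself, so I reproduce the power statement to confirm the setting. Inputs: "a total sample size of 90 evaluable patients (100 pts considering 10% of patients not evaluable after enrollment"), 1:1 allocation (45 evaluable per arm), one-sided alpha 0.025, responder rates 5% and 35%, SANDE difference 15, SD 20.

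- Schirmer, pooled z-test: null SE = √(2 × 0.20 × 0.80 / 45) = 0.0843; alternative SE = √((0.05 × 0.95 + 0.35 × 0.65) / 45) = 0.0782. Power = Φ((0.30 − 1.96 × 0.0843) / 0.0782) = Φ(1.72) = 95.8%, as stated.
- SANDE, t-test on 88 df: noncentrality = 15 / (20 × √(2/45)) = 3.56; power 94.0%, as stated.
- Product, taking the endpoints as independent: 0.958 × 0.940 = 0.9005, the stated 90%.

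None of this depends on the imputation code.

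**Rank of the fallback regression.** The illustrative data set has 50 patients per arm and 5 missing per arm, so 45 vehicle donors.

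| Model fitted to vehicle only | Columns | Rank |
|---|---|---|
| SANDE as coded: intercept, TRT, age class, sex | 4 | 3 |
| Schirmer as coded: the same plus baseline | 5 | 4 |
| SANDE without TRT | 3 | 3 |
| Schirmer without TRT | 4 | 4 |

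For the SANDE model, under four codings of TRT (effect, reference vehicle, reference cenegermin, numeric 1/2), the rank stayed at 3, the prediction for a vehicle patient was estimable, and the prediction for a cenegermin patient was not.

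**Why, in algebra.** Let TRT be coded t₂ for vehicle and t₁ for cenegermin, with intercept α and coefficient γ. The donors determine only a = α + γt₂. A cenegermin prediction needs α + γt₁ = a + γ(t₁ − t₂). Write g = γ(t₁ − t₂). The imputed value is the vehicle prediction plus g, and every g fits the donors equally well. Copy Reference as described in the prose is g = 0.

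**Non-uniqueness, shown once.** In the illustration the mean imputed SANDE for cenegermin was 46.6 with the term set to zero, equal to the vehicle mean. Minimum-norm solutions gave 18.8 (reference cenegermin) and −3.7 (effect coding). These values show only that the code has no single answer. They reflect my choice of solver and coding and say nothing about size in the trial.

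**How a nonzero g would carry through.** Assume that the planned 10% non-evaluable applies to the cenegermin arm and that all of it is monotone missing: 5 of 50. The arm mean for SANDE then moves by (5/50) × g = 0.1g. If g were as large as the planned 15-point difference, the shift would be 1.5 points. For Schirmer, the arm's responder proportion could move by at most 5/50 = 10 percentage points, against a planned difference of 30.

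**Covariates in the same statements.** Set against the prose, the SANDE REG statement lacks baseline and weeks 2, 4 and 8, and the Schirmer statement lacks week 2. Deleting TRT alone would leave SANDE imputed from age class and sex only.

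**The case against.** The strongest reply is that the plan settles the result in words. SAP 10.1.2.1 says that cenegermin values come from vehicle data and carry no effect beyond vehicle. Protocol 9.4.3.1, read to the end of its sentence, washes out treatment. A cenegermin imputation different from the vehicle prediction would breach the SAP, whatever the appendix code did. SAP 7.11 fixes the software as SAS 9.4 or later, and if that program zeroes an aliased term the code does what the prose says. A failed step or an absurd imputed mean would probably be noticed. The fallback may not be used at all: the documents give no expected number of retrieved dropouts.

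Most of this stands, and it limits the point. A reader might infer that the fallback for both co-primaries is undefined. The documents do not support that, because the prose defines the target and vehicle-arm imputations are unaffected. A reader might also infer a bias of known size or direction in favour of cenegermin. That is not supported either: g has no predictable value, and it may be zero.

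What the reply does not remove is that the code reaches the target through a software default that neither document states. The covariate gap does not depend on software behaviour.

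**Conclusion.** The point holds as a code correction of modest importance. In both alternative blocks TRT is redundant and inestimable, so the code does not by itself guarantee the imputation that SAP 10.1.2.1 describes. The numerical effect is nil if the software sets the aliased term to zero; otherwise the documents do not determine it. It arises only if MI-RD is abandoned and cenegermin patients have monotone missing data, about 5 patients under the 10% assumption above. I did not test how PROC MI treats the aliased term.

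**What to change.** In the alternative code of SAP 15.5.1 and 15.5.2, remove TRT from the MONOTONE REG statement and from the VAR list, and keep it in CLASS so that MODELOBS can select the vehicle donors. Add one sentence to 10.1.2 saying that the Copy Reference regression contains no treatment term. A cenegermin patient then receives the vehicle prediction by construction.

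In the same edit, bring the REG covariates into line with 10.1.2.1 and 10.1.2.2: add week 2 for Schirmer, and baseline and weeks 2, 4 and 8 for SANDE. With an intercept that makes 5 columns for Schirmer and 7 for SANDE, against roughly 45 vehicle donors.

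The cost is a few terms in two code blocks and one SAP sentence. Sample size, power and data collection do not change. A run on dummy data before database lock would confirm that the revised blocks execute.

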7.1 General

All patient data collected during the study will be listed by patient and site.

Appropriate descriptive statistics will be produced by treatment arms according to the nature of the variable.

For continuous data, number of observations, mean, standard deviation, median, range (minimum and maximum) and 95% confidence intervals will be presented.

For categorical data, frequency distributions and percentages with 95% confidence intervals (Wilson method) per category will be presented.

For primary analysis, the threshold for claiming statistical significance will 0.025 one-sided. For other analysis, unless otherwise specified, the significance level for statistical testing will be 0.05 and two-sided tests.

The statistical analyses (both descriptive and inferential) of some endpoints will be done on the eligible eye when applicable. Details will be provided in the statistical analysis outputs as notes.

Additional post-hoc analysis may be produced to further allow comparison between treatment and control, according to the results obtained. Any deviations from the original statistical plan (including unplanned analyses) will be documented in the CSR.

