10.1 Analysis of primary efficacy endpoint

10.1.1 Testing strategy and multiplicity adjustment

The following null hypothesis is defined on the first primary endpoint: the proportion of patients reaching a value of Schirmer I test (without anesthesia) $>10\text{mm}/5\text{min}$ at week 4 in cenegegermin (rhNGF) is lower or equal than control:

$$H_{01}: T_{\text{rhNGF}} \leq T_{\text{CONTROL}}$$

$$H_{11}: T_{\text{rhNGF}} > T_{\text{CONTROL}}$$

where T_{rhNGF} and T_{CONTROL} are the proportion of patients reaching a value of Schirmer I test (without anesthesia) $>10\text{mm}/5\text{min}$ at week 4 for cenegegermin and control groups, respectively. The null hypothesis H_{01} will be rejected if the associated primary analysis p-value will be lower than 0.025.

Similarly, the following null hypothesis is defined on the co-primary endpoint: the change from baseline (reduction) in the global SANDE score at week 12 in cenegegermin is lower or equal than control:

$$H_{02}: \mu_{\text{rhNGF}} \leq \mu_{\text{CONTROL}}$$

$$H_{12}: \mu_{\text{rhNGF}} > \mu_{\text{CONTROL}}$$

where μ_{rhNGF} and μ_{CONTROL} are the change from baseline (reduction) in the global SANDE score at week 12 for cenegegermin and control groups, respectively. The null hypothesis H_{02} will be rejected if the associated primary analysis p-value will be lower than 0.025.

Both null hypotheses H_{01} and H_{02} must be rejected to claim superiority of cenegegermin over control. Consequently, no multiplicity correction of type I error will be applied on primary endpoints analysis.

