3. Each of the 200 imputed datasets will be analyzed using observed and imputed data. Rubin's rule will be used for combining results to draw inference.

If there are not enough retrieved dropouts for convergence of MI-RD regression model, a Copy Reference approach will be adopted to consider a MNAR mechanism for missing data. The final decision on the use of the MI-RD vs Copy-Reference for this endpoint will be done at the time of the analysis and reported in the CSR.

Whether for MI-RD or Copy-Reference approach, the adjusted estimated treatment differences in means for global SANDE score between cenegeerin and vehicle at week 12 will be displayed together with the corresponding two-side 95% confidence intervals and p-value.

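### The SANDE pooling code gives no complete-data degrees of freedom, so the test uses in effect 1.960 where the ANCOVA supports about 1.988; the effect is small and arises with nearly complete data

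*SAP*

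**What the plan says.** SAP 7.1 sets the standard: "For primary analysis, the threshold for claiming statistical significance will 0.025 one-sided". SAP 10.1.1 adds that each co-primary null hypothesis "will be rejected if the associated primary analysis p-value will be lower than 0.025". For SANDE, SAP 10.1.2.2 specifies an ANCOVA with gender, age class and baseline score as fixed effects and site as a random effect, fitted to each of 200 imputed datasets. On pooling it says only "Rubin's rule will be used for combining results to draw inference".

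The one place where pooling is specified in detail is the code in SAP 15.5.2. There the contrast from PROC MIXED is combined with "PROC MIANALYZE DATA = DIFFS ; MODELEFFECTS ESTIMATE; STDERR STDERR; RUN". No `EDF=` option appears, and no SAP section names a degrees-of-freedom method or a small-sample adjustment.

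SAP section 5 plans for "a total sample size of 90 evaluable patients (100 pts considering 10% of patients not evaluable after enrollment") and states: "A power of 94.0% is achieved for SANDE primary endpoint".

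**The concern.** With many imputations, Rubin's original df formula reflects only the noise from imputing. It ignores the fact that the residual variance is itself estimated from about 100 patients. Unless the procedure is told the complete-data df, the pooled statistic is referred to a t distribution with thousands of df, which is a normal distribution in all but name. When little is missing, the test is then slightly too liberal and the confidence interval slightly too narrow.

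At stake is whether a confirmatory co-primary is tested at the level the SAP states. The SAP works to fine precision (the tipping-point rule in 10.1.3 uses a threshold of 0.02500), and a shift from 1.99 to 1.96 can turn a borderline result.

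**Working it through.** **Inputs from the documents**
- One-sided alpha 0.025 (SAP 7.1, 10.1.1); 200 imputations (SAP 10.1.2.2, 15.5.2).
- 90 evaluable and 100 enrolled patients, "randomization ratio 1:1"; "15 points in Global SANDE score improvement at Week 12, with a standard deviation of 20 points" (SAP section 5).
- Model: intercept, treatment, age, sex and baseline, plus a random site intercept (SAP 15.5.2). About 10 sites (protocol synopsis).
- The primary analysis is on the FAS with missing values imputed (SAP 7.2.4, 10.1.2.2), so about 100 patients enter each ANCOVA, not 90.

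**Assumptions not in the documents**
- Without `EDF=`, the complete-data df are taken as infinite.
- PROC MIXED uses its default containment df.
- There are exactly 10 sites and 100 patients in the FAS.

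**1. The plan's own figure.** With 45 per arm, the noncentrality is 15 / (20 × √(2/45)) = 3.558. Power from the noncentral t with 88 df is 94.04%; from the normal it is 94.49%. The stated 94.0% is reproduced.

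**2. Complete-data df.** Five fixed-effect parameters plus 10 site effects, less one redundancy, have rank 14. So df = 100 − 14 = 86, with critical value 1.988.

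**3. Df as coded.** Rubin's df are ν = (m − 1)(1 + 1/r)², with m = 200 and r the between- to within-imputation variance ratio. The Barnard-Rubin df are 1/(1/ν + 1/ν_obs), where ν_obs = [(86 + 1)/(86 + 3)] × 86 × (1 − γ) and γ = r/(1 + r).

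| r | Rubin df | critical value as coded | Barnard-Rubin df | critical value |
|---|---|---|---|---|
| 0.05 | 87,759 | 1.960 | 80.0 | 1.990 |
| 0.1 | 24,079 | 1.960 | 76.2 | 1.992 |
| 0.2 | 7,164 | 1.960 | 69.4 | 1.995 |
| 0.5 | 1,791 | 1.961 | 54.3 | 2.005 |

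**4. Tail area with complete data.** P(t₈₆ > 1.960) = 0.0266. Two-sided coverage is 1 − 2 × 0.0266 = 94.7%.

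**5. Null simulation, complete data** (N = 100, 10 sites, random intercept, 40,000 runs, Monte Carlo SE 0.0008). Against 1.960 the level was 0.0274 (intraclass correlation 0) and 0.0265 (0.1). Against t with 86 df it was 0.0255 and 0.0251. A separate simulation gave 0.0261 as coded and 0.0244 with 86 df.

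**6. Null simulation with missing data, pooled as coded.** The main runs used N = 100 and least squares without site; the missingness rates and retrieved-dropout counts are assumed. The MAR and Copy Reference runs used 60 imputations and 20,000 replicates (SE 0.0011). The MI-RD runs used 200 imputations and 8,000 replicates (SE 0.0017).
- MAR by arm: 0.0260 at 3% missing, 0.0258 at 10%. Other runs ranged from 0.024 to 0.029.
- Copy Reference: 0.0232 at 3%, 0.0171 at 10%. Other runs gave 0.020 to 0.025 at 2%, 0.018 at 5%, and 0.013 to 0.019 at 10%.
- MI-RD with 8 to 20 retrieved dropouts and 3 to 10 missing patients: 0.013 to 0.022.

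**7. Effect of Barnard-Rubin df in the main runs.** MAR falls to 0.0246 and 0.0244, Copy Reference to 0.0219 and 0.0157, and MI-RD to between 0.012 and 0.020.

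**The case against.** The strongest objection is that 0.0266 is a tail area. It equals the rejection rate only if almost nothing is missing, while the SAP allows for 10% non-evaluable patients and plans MI-RD or Copy Reference imputation. Under those methods Rubin's variance overstates the sampling variance, the simulated levels as coded are below 0.025, and the proposed change lowers them a little further. This stands. It rules out a reading that a reader might otherwise take from the code, namely that the co-primary as planned runs at about 0.027 with intervals that are too narrow. The point is confined to nearly complete data and to the MAR sensitivity analysis, where the simulated excess is of the order of simulation error in several runs.

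Three further inferences are also unsupported.
- The closer match of 94.0% to a t calculation does not show that planning and analysis conflict. SAP section 5 names no test, the figure matches an unadjusted two-sample comparison, and the gap to the normal is 0.45 points.
- The same defect cannot be read directly into the key secondary analyses. SAP 15.5 gives code for the primary analysis only, and Rubin's rule as named in 10.2.2 does not exclude small-sample df. What can be said is that the SAP leaves the df unstated there.
- Taking 90 as the ANCOVA sample size (76 df, tail 0.0268) while also adding imputation variance counts the missing patients twice.

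Finally, both co-primaries must be rejected. If SANDE is null and Schirmer has its planned power, the false-claim rate with complete data is about 0.958 × 0.0266 = 0.0255, assuming independence.

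What remains against dropping the point is that the conservatism is a by-product of how much is missing and how it is imputed. It is not a stated safeguard, and the better the retention that the protocol and SAP seek, the less of it there is.

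**Conclusion.** The reference distribution in the SANDE pooling code is mis-specified, and the effect is small. As coded, the critical value is in effect 1.960, against about 1.988 for an ANCOVA with about 86 df. With complete or nearly complete data the one-sided level is about 0.0266 (an excess of about 6% of alpha: 0.0016/0.025). The MAR sensitivity analysis may show a similar small excess. Under the planned primary imputation with about 3 to 10% missing, the documents and simulations give no evidence of type I error inflation.

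This rests on the software default for omitted complete-data df, containment df, 100 FAS patients at 10 sites, and the simulation settings listed above. It is a minor point that does not threaten the trial's conclusions, but it is worth correcting.

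**What to change.** In SAP 15.5.2, add `EDF=` to the PROC MIANALYZE call for the SANDE contrast, using the PROC MIXED df of the treatment contrast, which the DIFFS output already holds. State in SAP 10.1.2.2, 10.1.3 and 10.2.2 that Barnard-Rubin df are used for all pooled continuous endpoints, so that the rule does not depend on code given for the primary analysis alone.

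The cost is one option and a sentence in each section. P-values rise very slightly. At the planned effect with 45 per arm, power moves from about 94.4% (noncentral t with 88 df, critical value 1.960) to 94.0%, a loss of roughly 0.3 to 0.4 of a percentage point. Under MI-RD or Copy Reference the test becomes very slightly more conservative than it already is; the change does not bring the level back to 0.025 there. No design element changes.
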